5.5 Follow-Up

Study patients will be followed through their first clinic appointment after treatment completion with the appropriate evaluations. Data collection will continue through completion of planned therapy, or until subject meets criteria for removal from protocol therapy or off –study criteria are met as outlined below. Patients who are removed from study per the protocol criteria below, or who withdraw from the study, will not be replaced but will be treated as part of the analysis using either an “intention to treat”, “last observation carried forward” or “by imputation of the missing values”.

Study evaluations will occur each time chemotherapy is received where Caphosol is administered.

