4.2 Patients Who Do Not Begin Study Treatment

If a patient is registered on the study, and is later found not able to begin the planned study treatment, for whatever reason, the patient will be removed from study and treated at the physician's discretion. Study data will be collected until the time of study removal. The reason for removal from study will be clearly indicated on the case report forms.

If a patient begins treatment, and then decides to come off of study for whatever reason, the patient must be followed per Section 6.1.

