5.1 Treatment Plan Schema

[figure not shown]

Table 1: Treatment Plan

Day	Agent/Procedure
Enrollment	Randomization to control arm or Caphosol arm
Day 1 of Chemotherapy	Start study diary IF on Caphosol Arm : Start Caphosol, 30 mL QID
Completion of Chemotherapy	Control Arm : Continue study diary and Biotene for 7 days after therapy completed AND until ANC > 500 after nadir or until mucositis resolution, whichever occurs later. Caphosol Arm : Continue Caphosol, Biotene, and study diary for 7 days after therapy completed AND until ANC > 500 after nadir or until resolution of oral mucositis; whichever occurs latest.

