5.4 Duration of Therapy

Caphosol will be initiated on Day 1 of scheduled cancer therapy and will continue for:

- 7 days after therapy completion

AND

- ANC > 500 after nadir (count recovery)*

OR

- Resolution of oral mucositis symptom*

*(whichever occurs last)

Caphosol will be continued each time the patient receives chemotherapy where eligibility criteria are met for patients randomized to Caphosol arm.

Caphosol will be discontinued for allergy or patient intolerance. Please see Section 5.6 for criteria for removal from protocol therapy and off study criteria.

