5.6 Criteria for Removal from Protocol Therapy and Off-Study Criteria

5.6.1 Criteria for Removal from Protocol Therapy

- Completion of planned Caphosol therapy (all eligible chemotherapy cycles have been completed)
- Physician determines it is in the patient's best interest
- Adverse Event/Side Effects/Complications which based on the treating physician or patient/family opinion warrant coming off protocol therapy
- Inevaluable
- Patient Intolerance/Refusal

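### Section 5.5 stops data collection at removal from protocol therapy, in conflict with other text, and picks no method for the missing grades; LOCF, one option, scores a pre-onset leaver as a non-event

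*Combined protocol and SAP*

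**What the plan says.** Section 5.5 makes two statements about how long patients are observed. Its first sentence reads "Study patients will be followed through their first clinic appointment after treatment completion". The next sentence sets the end of data capture: "Data collection will continue through completion of planned therapy, or until subject meets criteria for removal from protocol therapy", or until off-study criteria are met.

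The removal criteria in 5.6.1 include physician decision, side effects, being inevaluable and "Patient Intolerance/Refusal". Section 5.4 adds, for one arm only, "Caphosol will be discontinued for allergy or patient intolerance". Section 5.6.2 lists the off-study criteria separately: death, loss to follow-up and withdrawal of consent to supply further data.

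Section 4.2 says of a patient who starts treatment and then comes off study that "the patient must be followed per Section 6.1". There is no Section 6.1. Section 6.0 is the study calendar and has no subsections.

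Under 5.5, removed or withdrawn patients are not replaced and stay in the analysis by one of three routes: intention to treat, "last observation carried forward", or imputation. No order or choice rule is given. Sections 10.1 to 10.3 do not choose either. Section 10.2 sets the primary analysis as Grade 1 versus Grade 2 or higher and says that loss to follow-up is not expected.

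**The concern.** The plan separates stopping the rinse from stopping data in 5.6, but 5.5 ends data capture at either event. A patient who declines the rinse may still attend for chemotherapy and could be graded, yet 5.5 as written leaves that outcome uncollected.

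The three options are not true alternatives. Intention to treat settles who is analysed and in which arm; it cannot supply a grade that was never recorded. LOCF does supply one, but it suits a prevention endpoint badly. Section 1.0 puts typical onset at days 7-14 of a course, and Section 6.0 requires a pre-study grade. An early leaver therefore usually carries forward a grade below 2 and counts as a prevention success.

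Two things are at stake. Primary outcomes would be lost that could have been collected, and the primary result could depend on a method chosen after the data are seen.

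**Working it through.** **Inputs from the documents.** 48 per arm, alpha 0.05, power 80%, a 30% difference, incidence range 25% to 50% (Section 10.3); binary endpoint with logistic analysis, or Fisher's exact test if numbers are small (10.2); typical onset at days 7-14 (1.0).

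**Assumed, because the documents are silent.** Two-sided testing; the pairs of rates compared; all exit rates; leavers have the average risk of their arm; the endpoint is any Grade 2 or higher during the observation period. Exit here means leaving before any Grade 2 or higher. Uncorrected chi-square stands in for the large-sample test.

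**The plan's own figure.** Take 55% v 25%, an absolute difference of 30 points, with mean rate 0.40:

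n = [1.96 × √(2 × 0.40 × 0.60) + 0.8416 × √(0.55 × 0.45 + 0.25 × 0.75)]² / 0.30² = (1.358 + 0.555)² / 0.09 = 40.7, so 41 per arm.

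With continuity correction: (40.66/4) × [1 + √(1 + 4/(40.66 × 0.30))]² = 47.1, so 48 per arm. The stated 48 is reproduced under this pair. It contains no allowance for missing outcomes.

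**Effect of LOCF.** If a fraction d of an arm leaves before onset and is scored below Grade 2, then observed rate = true rate × (1 − d). Counting only recorded events over all randomised patients gives the same expression. Rejection rates below come from exact enumeration of all 49 × 49 outcomes at 48 per arm.

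No true effect (rejection in either direction, chi-square/Fisher):

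| Exit, control v Caphosol | True rate 50%: observed rates | Rejection | True rate 25%: observed rates | Rejection |
|---|---|---|---|---|
| 0% v 0% | 50.0 v 50.0% | 5.2/3.2% | 25.0 v 25.0% | 5.1/2.9% |
| 0% v 5% | 50.0 v 47.5% | 5.9/3.7% | 25.0 v 23.75% | 5.3/3.0% |
| 5% v 10% | 47.5 v 45.0% | 5.8/3.6% | 23.75 v 22.5% | 5.3/3.0% |
| 0% v 10% | 50.0 v 45.0% | 8.0/5.2% | 25.0 v 22.5% | 6.0/3.5% |
| 0% v 20% | 50.0 v 40.0% | 16.8/12.1% | 25.0 v 20.0% | 9.0/5.6% |

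With the arms reversed, 10% v 0% at a true rate of 50% also gives 8.0/5.2%, now with 5 points against Caphosol. Equal exit of 10% gives 5.1/3.1%, so no inflation.

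True effect 55% v 25%, equal exit in both arms (power, chi-square/Fisher):

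| Exit | Full data | Leavers omitted | LOCF |
|---|---|---|---|
| 10% | 86.3/80.8% | 83.6/76.9% (43 per arm) | 80.0/72.8% |
| 20% | 86.3/80.8% | 77.2/69.6% (38 per arm) | 73.1/64.5% |

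At 20% exit, the loss from missing outcomes is 86.3 − 77.2 = 9.1 points (chi-square) and 80.8 − 69.6 = 11.2 (Fisher). LOCF adds 77.2 − 73.1 = 4.1 and 69.6 − 64.5 = 5.1. At 10% exit the two parts are closer: 2.7 and 3.6 points (chi-square), 3.9 and 4.1 (Fisher).

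**The case against.** The strongest reply is that 5.5 is muddled, not a settled decision to stop collecting. Its first sentence follows patients past treatment completion. Section 4.2 requires follow-up, and its missing reference may be a slip for the calendar in 6.0, with its at-least-weekly evaluations. This stands: the defect is a contradiction to be reconciled. It does not cure 5.5, because the only explicit rule on when data capture ends is the one that ends it at removal.

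Second, the exposed group may be small. Treatment spans repeated eligible cycles (5.4), so a patient who leaves after a full cycle already has grades over the usual onset window. Anyone with a recorded Grade 2 or higher before exit is unaffected if the endpoint is any such grade. Side effects are not expected (7.1.7, 8.2), nor is loss to follow-up (10.2). This also stands, although those statements do not cover refusal or physician removal, where 5.5 itself stops collection.

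Third, LOCF is not the only route to the mis-scoring, and it does not cause the whole power loss. The working bears out both points, so deleting LOCF alone would not be enough.

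A reader might also infer from "Study evaluations will occur each time chemotherapy is received where Caphosol is administered" that controls are not evaluated. The documents do not support that. Section 5.0 lists observations for both arms, Table 1 tells controls "Continue study diary and Biotene for 7 days after therapy completed", and the calendar in 6.0 makes no distinction by arm. It is a matter of wording only.

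**Conclusion.** The point holds as a conflict in the text that, followed literally, produces avoidable missing primary outcomes, together with an unspecified method for handling them.

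A reader might go further and infer that the plan is biased in favour of Caphosol. The documents do not support that. LOCF scores early leavers as non-events in both arms. It favours Caphosol only if pre-onset exit is commoner there, which is possible given the added rinse and the arm-specific discontinuation rule. It works against Caphosol if exit is commoner in controls, and equal exit gives no false-positive inflation but dilutes a true effect. No exit rate is given, so direction and size are unknown.

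Under the assumed scenarios, a modest imbalance moves the false-positive rate little. Fisher's test stays at or below 5.2% up to 0% v 10% exit; clear inflation, to 16.8/12.1%, needs 0% v 20% at 50% incidence. For power at equal 20% exit, most of the loss comes from the missing outcomes and about 4-5 points from LOCF. These figures rest on average-risk leavers and an any-Grade-2-or-higher endpoint, neither of which the documents state. The case for change is that the data loss is avoidable and the method is left open, not that a large bias is likely.

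**What to change.** - In 5.5, continue mucositis grading and data collection for every randomised patient through the planned observation period whether or not the study rinse has stopped, ending only for a 5.6.2 criterion.
- Reconcile the second paragraph of 4.2 with this and correct its reference to Section 6.1.
- In Section 10, analyse all randomised patients in their assigned arm.
- Delete LOCF and name one primary method for grades that are still missing, for example multiple imputation by arm using prior grades and chemotherapy agent. Add a sensitivity analysis that varies the missing-outcome assumption in both arms.
- Report the timing of and reasons for exit by arm.

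The cost is protocol and SAP wording plus some extra grading and data entry, largely within the at-least-weekly evaluations already planned in Section 6.0. Patients who refuse further contact will still have missing grades, so the imputation and sensitivity analysis remain necessary.

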5.6 Criteria for Removal from Protocol Therapy and Off-Study Criteria

5.6.1 Criteria for Removal from Protocol Therapy

- Completion of planned Caphosol therapy (all eligible chemotherapy cycles have been completed)
- Physician determines it is in the patient's best interest
- Adverse Event/Side Effects/Complications which based on the treating physician or patient/family opinion warrant coming off protocol therapy
- Inevaluable
- Patient Intolerance/Refusal

5.6.2 Off-Study Criteria

- Death
- Lost to follow-up
- Withdrawal of consent for any further data submission

6.0 STUDY CALENDAR

Table 2: Required Evaluations*

Evaluations	Pre-Study	Treatment Period
Clinical history	X	Weekly
Physical exam	X	Weekly
Vital exam	X	Weekly
Weight	X	
Height	X	
Performance status	X	Weekly
Oral mucositis grading	X	X
Study diary		Daily
At Each Clinic Visit		
- Oral mucositis grading		X
- Age-appropriate pain scale		X
- Assessment of narcotic use		X
For Patients Requiring Admission		
- Oral mucositis grading		Daily
- Age-appropriate pain scale		Daily
- Assessment of narcotic use		Daily
- Nutrition assessment		Daily

**Patient evaluations (inpatient and outpatient) will occur at least weekly and be collected by the study nurses and entered into the patient's medical record (EPIC) under a separate progress note as well as recorded in the protocol specific electronic case report forms (eCRF) in Oncore.*

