Caphosol (Jazz Pharmaceuticals, Inc. Palo Alto, CA) is a supersaturated aqueous electrolyte solution comprised of sodium phosphate, calcium chloride and sodium chloride, resembling human saliva that was designed in part to replace the normal ionic and pH balance of the oral cavity and been used to prevent and/or treat oral mucositis. Caphosol is hypothesized to diffuse into epithelial intracellular spaces and permeate mucosal lesions in oral mucositis. In addition, calcium may modulate the inflammatory response and tissue repair processes and phosphate may be involved in repairing damage to the mucosal surface. In a 2013 review article by Quinn et al., 24 of the 30 studies reviewed found Caphosol to be beneficial for the prevention and treatment of oral mucositis in patients receiving high-dose chemotherapy and/or radiotherapy (13). The author concluded that despite the heterogeneous nature of the reviewed studies, with many involving small patient numbers, involving single-centers and including historical controls, the data supported strong consideration for the addition of Caphosol to oral mucositis prevention and treatment plans. The largest, randomized study of Caphosol for the prevention and treatment of oral mucositis was a double blind adult study comparing Caphosol to fluoride therapy in 95 allogeneic and autologous hematopoietic stem cell transplant recipients (14). This 2003 study by Papas and colleagues, they reported that 40% of patients in the Caphosol arm had no mucositis compared with 19% in the control arm. Also, patients in the Caphosol arm had significantly fewer mean days of mucositis (3.72 vs. 7.22; $p=0.001$), duration of pain (2.86 vs. 7.67; $p=0.0001$), days receiving morphine (1.26 vs. 4.02; $p=0.0001$), dose of morphine (34.54 mg vs. 122.78 mg; $p=0.0001$) and days to the onset of neutrophil recovery $>200 \text{ mm}^3$ (11.12 vs. 12.56; $p=0.00173$) (14).

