2.0 STUDY OVERVIEW

Eligible patients will be identified in the oncology clinic and/or the oncology ward and consented/enrolled on study. Study patients randomized to the Caphosol arm will begin Caphosol therapy prior to administration of systemic chemotherapy on Day 1 according to protocol. Caphosol administration will continue through the planned chemotherapy administration and until stopping criteria are met. Chemotherapy will be administered either in the MACC Fund Center or the inpatient service. Once the chemotherapy is complete the patient will be discharged to home and followed in the MACC Fund Center at regular intervals as dictated by standards of care. Caphosol treatment will continue at home as outlined in the protocol for 7 days following completion of chemotherapy and adequate neutrophil recovery, or until oral mucositis symptoms resolve, whichever occurs later. In the event the patient requires hospital admission, Caphosol treatment will continue according to protocol. The patient/family will keep a daily drug diary of administration of Caphosol throughout each cycle which will be reviewed by the study team at

each study visit. As well patients in each cohort will record in their diary other oral topical agents they are using and any narcotic and non-narcotic medications used for treatment of pain/mucositis.

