- Incidence of oral mucositis. Oral mucositis will be defined and characterized by the Common Terminology Criteria for Adverse Events (CTCAE) Version 4.0 as Grade 1-4.
- Severity of oral mucositis, according to:
 - Age-appropriate pain scales (LIKERT and FACES)
 - CTCAE V 4.0 grading
 - Total narcotic usage (both the total amounts in milligrams and the number of days the patient required intravenous narcotic therapy as well as any increase of dose above baseline for patients who are on scheduled chronic use of narcotics)
 - Number of hospital days with oral mucositis present
 - TPN use and duration

The following will be observed on all patients on the Caphosol arm, via the study diary:

- Missed doses of Caphosol and reason
- Side effects attributed to Caphosol therapy
- Use of any other oral topical agents for oral mucositis (dose, schedule, number of doses taken) such as biotene/ chlorhexidine rinses and/or magic mouthwash.
- Use of any non-narcotic pain medications for oral mucositis (dose, schedule, number of doses taken)
- Use of any narcotics for oral mucositis (dose, schedule, number of doses taken)

The following will be observed on all patients on the Biotene arm, via the study diary:

- Use of any other oral topical agents for oral mucositis (dose, schedule, number of doses taken) such as chlorhexidine rinses and/or magic mouthwash.
- Use of any non-narcotic pain medications for oral mucositis (dose, schedule, number of doses taken)
- Use of any narcotics for oral mucositis (dose, schedule, number of doses taken)

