10.2 Statistical Analysis

Comparisons of binary outcomes such as prevention of oral mucositis will use logistic analysis or Fisher's exact test if the numbers are small. Comparisons of the severity of oral mucositis (an ordinal scale) will use the Wilcoxon rank sum test since the data is on a 5 point Likert scale, although there are really only two levels of values. Similarly for the secondary outcome an ordinal pain scale can be treated as an ordinal scale. Length of stay and duration of TPN will use a t-test plus a log transform, if necessary to reduce the skewness of the data. Otherwise the Wilcoxon test will be used.

Although there may be loss to follow-up, we don't expect it because continued

chemotherapy depends on the clearing of the mucositis.

The primary analysis for mucositis will be based on a binary scale (Grade 1 versus Grade ≥ 2 mucositis) because the mucositis essentially has only two clinically pieces to the scale. It also represents common clinical practice.

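### Outpatient mucositis is graded only at clinic visits, with no rule for the days between, so short Grade ≥2 episodes can be missed and a shortening effect could partly be scored as prevention

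*Combined protocol and SAP*

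**What the plan says.** **Endpoint.** Section 10.2 makes the primary comparison binary: "The primary analysis for mucositis will be based on a binary scale (Grade 1 versus Grade ≥ 2 mucositis". Section 2.1 states the aim as preventing Grade ≥2 mucositis.

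**Grading schedule.** Table 2 (section 6.0) has two regimes. Under "For Patients Requiring Admission", mucositis grade, pain scale and narcotic use are recorded daily. Under "At Each Clinic Visit", the same items carry a cross and no interval. The general mucositis-grading row also has only a cross. The footnote sets the floor: "Patient evaluations (inpatient and outpatient) will occur at least weekly and be collected by the study nurses". Section 2.0 leaves the actual visit interval open: after chemotherapy, patients go home and are "followed in the MACC Fund Center at regular intervals as dictated by standards of care".

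**Time at home.** Rinsing continues for at least 7 days after chemotherapy ends (sections 2.0 and 5.4). The Background puts typical onset at 7 to 14 days into a course. Much of the risk period can therefore fall outside hospital.

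**Diary.** It is kept daily in both arms. Section 2.0 says "patients in each cohort will record in their diary other oral topical agents they are using", together with narcotic and non-narcotic medicines for pain or mucositis. Section 5.0 repeats this for each arm and adds missed doses and side effects for Caphosol. Neither list includes mouth pain or diet, although the CTCAE definition of Grade 2 in the Background rests on moderate pain and a modified diet.

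**What is not stated.** No section says that a visit grade is the worst since the last one, that the diary feeds into grading, or how an episode between visits is scored.

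**The concern.** If each visit grade describes only the day of the visit, an outpatient episode that begins and ends between visits is recorded as no event. The chance of recording an episode then depends on how long it lasts and on whether the patient is in hospital.

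The protocol gives reason to think that Caphosol could change both. The Background cites an adult transplant trial with "significantly fewer mean days of mucositis (3.72 vs. 7.22" days, Caphosol v control. Section 2.1 hypothesises fewer days in hospital. Detection could therefore differ between arms as a result of treatment, and randomisation does not remove such a difference.

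Two things are at stake. The first is interpretation: a shorter course of mucositis could be read in part as prevention, which is the primary claim. The second is power: missed episodes in both arms shrink the observable difference even when episode length does not depend on treatment.

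**Working it through.** **1. The plan's own figure.** Section 10.3 gives alpha 0.05, power 80% and 48 per group for a 30% difference, with a mucositis range of 25% to 50%. It states neither the pair of rates nor the sidedness. I assume a two-sided test and try 55% v 25%:
- n = [1.96·√(2·0.40·0.60) + 0.8416·√(0.55·0.45 + 0.25·0.75)]² / 0.30² = 40.7, so 41.
- With continuity correction: (40.7/4)·[1 + √(1 + 4/(40.7·0.30))]² = 47.1, so 48.

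The 48 is therefore consistent with a 30-point absolute difference. Below I use 50% v 20%, an assumed pair with the same difference.

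**2. Detection model (assumptions).** Visits fall every g days at random phase, and each affected patient has one episode.
- Fixed length d: detection = min(1, d/g).
- Exponential lengths with mean d: detection = (d/g)(1 − e^(−g/d)).
- Observed rate = true rate × detection.

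Rejection rates come from exact binomial enumeration of the two-sided pooled z test with 48 per arm. With no true or observed difference at 50%, that test rejects about 5% of the time.

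**3. Power, equal fixed lengths in both arms, all outpatient, g = 7, true 50% v 20%.**

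| Episode length | Detection | Observed rates | Power |
|---|---|---|---|
| ≥7 days | 100% | 50.0% v 20.0% | 88% |
| 5 days | 71% | 35.7% v 14.3% | 70% |
| 4 days | 57% | 28.6% v 11.4% | 57% |

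**4. False rejection, equal true incidence of 50%, all outpatient, g = 7.** The Background gives mean days of 7.22 (control) and 3.72 (Caphosol), with 19% and 40% of patients free of mucositis. If those means include the unaffected patients, the lengths in affected patients are 7.22/0.81 = 8.9 and 3.72/0.60 = 6.2 days.

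| Lengths, control v Caphosol | Shape | Observed rates | Rejection |
|---|---|---|---|
| 8.9 v 6.2 | exponential | 34.6% v 30.0% | 8% |
| 8.9 v 6.2 | fixed | 50.0% v 44.3% | 9% |
| 7.22 v 3.72 | exponential | 32.0% v 22.5% | 18% |
| 7.22 v 3.72 | fixed | 50.0% v 26.6% | 66% |

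**5. What moves the 66% case.**
- Visit gap: at 5 days, detection on Caphosol is 3.72/5 = 74% and rejection is 25%. At 3.5 days, detection is complete and rejection is about 5%.
- Share of cases graded daily, equal in both arms: rejection is 42%, 21% and 9% at shares of 25%, 50% and 75%. The fall is not linear. Halving the excess over 5% would give about 36%, not 21%.
- Repeated episodes in the same affected patients, with the event taken as ever Grade ≥2: two independent episodes give detection 1 − (1 − 0.531)² = 78% and rejection 19%; three give 90% and 8%. This holds the share of patients ever affected at 50%. If instead each cycle carries an independent 20% risk, the spurious difference grows, from 9 points after one cycle to 25 after six.
- Episodes of 7 days or more in both arms: no spurious difference.

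**6. Admission alone.** Take equal incidence of 50%, 4-day episodes in both arms, and assumed admitted shares of 60% (control) and 20% (Caphosol).
- Control: 0.5·(0.6 + 0.4·4/7) = 41.4%.
- Caphosol: 0.5·(0.2 + 0.8·4/7) = 32.9%.
- Rejection is 14%.

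Over admitted shares from 50%/25% to 80%/20%, lengths of 3 to 5 days and true incidence of 40% or 50%, the spurious difference is 3 to 17 points.

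**The case against.** **Weekly is a floor, not the schedule.** Every clinic visit is graded, and visits may be more frequent. This stands. The 7-day results describe the sparsest permitted schedule, and the fixed-length bias is gone at 3.5 days. With exponential lengths of 7.22 v 3.72 days, however, about 11% rejection remains at 3.5 days.

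**The diary and history already carry information.** Both arms record topical agents and analgesics taken for mucositis, the study team reviews the drug diary at visits, and clinical history is taken weekly. The Caphosol diary also logs administration, which may be stepped up with symptoms. A reader might infer that nothing captures mucositis between visits, and that would be too strong. The gap is narrower: no rule turns these entries into a grade, and mouth pain and diet are not among the listed items.

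**Softer mucositis is not a false result.** A reader might also infer that a rinse which merely softens mucositis would be miscounted. Mostly it would not be. Moving Grade 2 to Grade 1 is prevention of the defined event, and moving Grade 3 to Grade 2 still counts as an event. Softening misleads only indirectly, when milder cases avoid admission and so lose daily grading.

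**The cited durations transfer poorly.** They come from adult transplant recipients, whom section 3.2 excludes, and cover mucositis of any grade. This stands, so the results are a range and not a forecast.

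**Diary-supported grading may add bias.** The control arm uses Biotene only and has no placebo, so families know the allocation. This stands as a cost of the fix, and it is why a sensitivity analysis without diary-supported grades is needed.

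**Conclusion.** The concern holds in conditional form. Detection of the primary event depends on episode length and on admission, and the plan has no rule to offset this. If Caphosol shortens episodes or reduces admissions, part of that effect could be scored as prevention.

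Under 7-day gaps and equal true incidence of 50%, false rejection is about 8% to 18% on the more plausible duration assumptions, against a nominal 5%. The 66% figure should not be taken as the expected size. It needs all cases to be outpatients, fixed lengths, the sparsest permitted visits and unadjusted durations from a population that this trial excludes. The documents also do not support saying that a shortening effect would necessarily be scored as prevention, because there is no such bias if Grade ≥2 episodes outlast the visit gap.

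The loss of power does not need a treatment effect on duration: 88% falls to about 70% or 57% with 5-day or 4-day outpatient episodes graded weekly.

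The documents give neither the length of Grade ≥2 episodes in this population, nor the usual visit interval, nor the share admitted. My point about the diary rests on its contents as listed in sections 2.0 and 5.0. Confidence is moderate. This is a cheap improvement that should be made, not a fatal flaw.

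**What to change.** 1. State in Table 2 that each clinic grade, assigned by the study nurse, is the worst CTCAE grade since the previous grading, using history and the diary.
2. Add one CTCAE-anchored item to the existing daily diary in both arms: mouth pain (none, mild, moderate, severe) and eating (normal, modified diet, unable to eat).
3. Define the primary event in section 10.2 as any Grade ≥2 graded in this way.
4. Report two sensitivity analyses: (a) visit-day and inpatient grades only, without diary-supported grades; (b) a common assessment schedule for all patients, admitted or not. State that (b) addresses only the imbalance due to admission. It does not remove the effect of shorter episodes.

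**Cost.** One diary line, one eCRF field, a one-line change to Table 2 and a sentence in section 10.2, with no extra visits or staff. The downside is that between-visit grades rest partly on patient or caregiver report, given by people who know the allocation. Nurse assignment limits this, and analysis (a) shows how much the result depends on it.
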